Statistical Analysis Plan (SAP)

Sweet Tooth: Nature or Nurture? Role of Long-term Dietary Sweetness Exposure on Sweetness Preferences

Version 2024.02.07 (yyyy.mm.dd)

GENERAL INFORMATION	
Principal investigator	Dr. [name] Sensory Science and Eating Behaviour Wageningen University and Research Wageningen, the Netherlands
Core team members	[name] [name] (Project leader) ¹ [name] (statistician) ¹ [name] ² [name] ¹ [name] ² [name] ² [name] ¹
	¹ Division of Human Nutrition and Health, Wageningen University and Research, Wageningen, The Netherlands
	² Department of Psychology, Faculty of Science and Technology, Bournemouth University, Bournemouth, United Kingdom
Name of project	Sweet Tooth
ClinicalTrials.gov identifier	NCT04497974
Project Registration number	NL72134.081.19
Ethical review	METC-nr 20/02, METC-WU

INTRODUCTION	
Objectives	
Primary objective: To assess the effect of a 6-month low, regular, and high dietary sweetness exposure on preference for sweet foods and beverages, and to compare these effects between the intervention groups.
 
Secondary Objective(s): To assess the effect of a 6-month low, regular, and high dietary sweetness exposure on taste intensity perception, behavioural outcomes: food choice and intake, sweet-like type, food cravings, dietary taste preferences, dietary taste patterns; anthropometric outcomes: body composition, waist-hip circumference, body weight; and biochemical outcomes: glucose variability, and biomarkers related to CVD and diabetes.

STUDY METHODS	
Trial design	
The Sweet Tooth study is a 6-month parallel randomized controlled trial with partial food provision. with three arms:
 
 1. a regular sweet exposure diet (RSE, control) (n=60); 2. a low sweetness exposure diet (LSE) (n=60); and 3. a high sweetness exposure diet (HSE) (n=60).

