Randomization	
Data collected at the screening visit are used to assign participants to intervention groups. Matched groups are randomized to the interventions to minimize differences between intervention groups in these baseline characteristics. Based on sex (2 levels: male, female), age (3 levels: 18–34, 35–49, 50–65), Body Mass Index (BMI) (2 levels: 18.5–24.9, 25–30 kg/m²) and sweet liker phenotype (3 levels: sweet liker, inverted U, sweet disliker), in a process of stratified randomization (2×3×2×3=36 strata). Treatment allocation is performed according to a computer-generated random schedule, at the ratio 1:1:1 to each of the three groups. Treatment allocation is performed by an independent person, not involved in the study outcome assessments or statistical analyses.

Sample size	
The sample size calculation is based on our primary outcome: change in preference score from 0–6 months. Previous studies have established that it is possible to detect shifts in preferred concentration from preference tests. For example, looking at the study of Liem and [name] (2004) and the change in most preferred concentration, we can observe that mean ranking score for the sweet exposure group changed by around 0.4 and by around 0.6 for the sour exposure group from baseline to after exposure, which is around 10%. Therefore, the effect size of 0.1 was considered to be a relevant and meaningful effect size for our study and was used to estimate the sample size. We estimate that 147 participants are needed to detect an effect size of 0.1, assuming a parallel study with 3 groups, with two repeated measures (baseline vs 6-month, correlation between measures of 0.7), and a

	power of 80% at a significance level of 0.05. To account for a potential dropout of 20%, 180 individuals will be enrolled in the study.																																																																																																																																																																																									
Statistical interim analysis	No interim analyses will be carried out.																																																																																																																																																																																									

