Adherence and Protocol deviations	Adherence to diets will be assessed on group level with biomarkers of sweetener consumption in 24-h urine sample, and 24h recalls.

STATISTICAL ANALYSIS	
Analysis methods	
Data will be analyzed in R. Based on findings of previous studies (Liem and [name], 2004), we do not expect the data to be non-normally distributed. Descriptive statistics will be provided for each of the three intervention groups at baseline and will include demographic, dietary and lifestyle information. Continuous data will be summarized using means, SD/SE and 95% confidence intervals or median/geometric means and back-transformed 95% CI's if not normally distributed. Categorical variables will be summarized using counts and percentages.
 
Analysis will be conducted on both an intention-to- treat (ITT) and a per-protocol basis. The ITT analysis will be the primary analysis. The per-protocol analysis (participants who finished the study), will help us determine whether the effects are the result of individuals adhering to the procedure and consuming the provided intervention foods. In the event of missing data due to drop-out, the outcome variables that have not been recorded will be treated as missing data. Unblinding will occur at the conclusion of the study to determine the effect of the intervention. Unblinding will take place in two steps: initially disclosing the allocation of individuals to their respective groups, without indicating intervention allocation. Only after the primary analyses have been conducted we will unblind the identity of each group.
 
Primary outcome:
 
To determine whether there is a shift in sweetness preference between baseline and month 6, statistical techniques appropriate for longitudinal data analysis, that is linear mixed effects models, will be used, with treatment (LSE, RSE and HSE), time (baseline, 1, 3, 6, 7 and 10-months) as fixed factors, the interaction between treatment x time outcome and participant number as a random factor. Our main interest is in the change in preference score between 0 and 6 months of any two intervention groups. The interaction effect will be evaluated to indicate if the change differed between the groups. If significant, the following predefined contrasts will be calculated: baseline vs. month 6 and LSE vs. RSE vs. HSE with all possible combinations. Subsequent, pairwise post-hoc tests will be Bonferroni adjusted.

Other outcomes:

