Similar linear mixed effects models will be used to explore effects of sweet taste exposure on the other dependent measures over time (baseline, 1, 3, 6, 7 and 10-months). The interaction effect (intervention group x time) will be evaluated to indicate if the pattern of change of a certain outcome differed between the groups. If significant, the following predefined contrasts will be calculated: baseline vs. 1 vs. 3 vs. 6 vs. 7 vs. 10-months and LSE vs. RSE vs. HSE with all possible combinations.

In light of the research in this area, we will explore differences between intervention groups and secondary outcome variables and explore related but separate questions of whether glucose variability, body composition, food cravings, blood biomarkers are related to sweetness exposure, age, gender, sweet liker status and BMI.

By comparing group means of urine extraction of urinary sucrose, fructose, and LCSs between intervention groups, the level of compliance will be evaluated. Linear mixed effects models will be adjusted for covariates where appropriate and both unadjusted and adjusted models will be reported. If interaction effect between time and intervention are identified, Posthoc tests (with Bonferroni adjustments) will be applied to identify statistically significant differences.

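### The between-arm differences in 0–6 month change, the plan's stated main interest, are planned only if the interaction is significant, so a null result comes with no planned estimate or interval

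*SAP*

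**What the plan says.** All of this is in the SAP.

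- **Statistical Analysis, Analysis methods, Primary outcome.** The quantity of interest is named: "Our main interest is in the change in preference score between 0 and 6 months of any two intervention groups". The model has "time (baseline, 1, 3, 6, 7 and 10-months) as fixed factors", together with treatment and the treatment-by-time interaction. The interaction is the test: "The interaction effect will be evaluated to indicate if the change differed between the groups". Then comes the condition: "If significant, the following predefined contrasts will be calculated: baseline vs. month 6 and LSE vs. RSE vs. HSE with all possible combinations". Multiplicity is handled by "Subsequent, pairwise post-hoc tests will be Bonferroni adjusted". No step is given for a non-significant interaction, and no interval is mentioned for the contrasts even when they are calculated.
- **Statistical Analysis, Other outcomes.** The same condition applies: "If significant, the following predefined contrasts will be calculated: baseline vs. 1 vs. 3 vs. 6 vs. 7 vs. 10-months", again with all arm combinations.
- **Study Methods, Sample size.** "the effect size of 0.1 was considered to be a relevant and meaningful effect size for our study". The value is used to set N and does not return in the analysis.
- **Introduction, Objectives.** The primary objective is to assess the effect of each exposure and compare the effects between arms. It carries no condition on a test result.

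The only intervals planned are 95% CIs in the general description of how continuous data will be summarised.

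**The concern.** The objective asks for a comparison on both branches of the test, and the analysis section plans one on only one branch. If the interaction is not significant, the plan does not say how far apart the arms were or how precisely that was measured. A trial that had pinned the differences close to zero and a trial too imprecise to say anything would then look alike on the primary comparison.

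There is a second cost on the other branch. If differences are shown only when the test succeeds, those shown are selected for being large and overstate the effect on average.

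This is not a detail that a SAP leaves to the protocol. The SAP states the rule itself.

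**Working it through.** **Inputs (SAP, Sample size).** Three groups, two measures, correlation 0.7, effect size 0.1, power 80%, alpha 0.05, N = 147, hence 147/3 = 49 per arm. The SAP gives no SD on the 0–100 scale, so results are in units of the single-visit SD.

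**1. Reproducing the plan's N.** Read 0.1 as Cohen's f in a repeated-measures within-between interaction.
- Noncentrality = f² × N × m/(1 − ρ) = 0.01 × 147 × 2/0.3 = 9.8, with 2 and 144 df.
- Power is 79.8%, so 147 is reproduced. The SAP does not label the 0.1; this reading is adopted because it returns the stated N.

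**2. Precision of a difference in change.**
- SD of change = √(2 × (1 − 0.7)) = 0.775.
- SE of a difference = 0.775 × √(2/49) = 0.156.
- 95% half-width = 1.977 × 0.1565 = 0.31 SD. Bonferroni for three pairs: 2.42 × 0.1565 = 0.38 SD.

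**3. What f = 0.1 means between arms.** It fixes no single difference.
- Evenly spaced changes (−d, 0, d): f² = d²/6, so d = √0.06 = 0.245. Outer arms differ by 0.49 SD, adjacent arms by 0.245 SD.
- One arm apart, changes (−2b, b, b): f² = b²/2, so b = √0.02 = 0.141. The largest difference is 3b = 0.42 SD.

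**4. How often the plan stops without a contrast.**
- No true effect: about 95% of trials.
- At the planned effect, 2-df test: about 20%.
- The interaction as specified has six time points and so 2 × 5 = 10 df. Assuming compound symmetry and 147 completers, the rate is again about 20% if the effect is present at month 6 only, and about 25% if it builds to month 6 and then fades (assumed patterns).

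**5. What the unplanned interval could show if the arms do not differ.** Over all trials, the chance that the HSE–LSE interval lies wholly within ±M is 2Φ(M/SE − c) − 1. For M = 0.49 and c = 1.977: 2Φ(3.13 − 1.977) − 1 = 75%. The last column restricts to non-significant trials by simulation (2-df test).

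| Largest difference M | Interval | All trials | Non-significant trials |
|---|---|---|---|
| 0.49 SD | 95% | 75% | about 78% |
| 0.49 SD | Bonferroni | 52% | about 54% |
| 0.42 SD | 95% | 54% | about 55–56% |
| 0.42 SD | Bonferroni | 23% | about 24% |
| 0.245 SD | either | 0% | 0% |

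The last row is plain arithmetic: the full width 2 × 0.31 = 0.62 SD cannot fit inside 2 × 0.245 = 0.49 SD.

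If the true HSE–LSE difference is 0.49 SD, about 12% of non-significant trials would show an unadjusted interval wholly within ±0.49 SD, against about 78% when there is no difference. That contrast holds for this pair, evenly spaced arms and unadjusted intervals.

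**6. Bias after significance.** With a true HSE–LSE difference of 0.49 SD, the mean estimate among significant trials is 0.54 SD, and 0.54/0.49 = 1.10, an overstatement of about 10%.

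**The case against.** The best reply is that the plan is silent on an estimate after a null test and does not forbid one. Group means with 95% CIs are planned, and the sentence is not expressly limited to baseline. Under Other outcomes the SAP says that unadjusted and adjusted models will both be reported; with RSE and baseline as reference levels, the month-6 interaction coefficients are the LSE–RSE and HSE–RSE differences in change. Nothing is lost from the data, since the fitted model contains every contrast.

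Much of this stands as a limit on the point. A reader might infer that a null trial would report only a p-value; that is too strong, because group summaries with intervals are planned. But group intervals do not give the interval for a between-arm difference in change, since they do not carry the within-person correlation. The sentence on reporting models has unclear scope and commits to no month-6 difference or interval. Recovering the contrasts after a null test would mean going beyond the plan with the result known and no interval level fixed in advance.

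Gating can also be defended as multiplicity control. That justifies gating significance claims; it does not require withholding estimates.

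Finally, the size of the gain depends on assumptions. The 78% is the most favourable case, and at this N neither comparison with control could exclude an adjacent-arm difference of 0.245 SD in both directions.

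**Conclusion.** The point holds. The SAP makes its stated main comparison conditional on a significant interaction, repeats the condition for the other outcomes, and plans no between-arm difference in change or interval otherwise. The interval would have a 95% half-width of 0.31 SD (0.38 SD with Bonferroni) against a largest planned difference of 0.42–0.49 SD. In non-significant trials with no true difference it would exclude that difference for HSE–LSE in about 24% to 78% of cases. These figures rest on 49 evaluable per arm, correlation 0.7, 0.1 read as Cohen's f, and the two arm patterns shown. They affect how often a null would be informative; the case for reporting does not depend on them, because a wide interval is itself the evidence that a null is inconclusive.

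Two stronger readings are not supported:

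- From the title, "Sweet Tooth: Nature or Nurture? Role of Long-term Dietary Sweetness Exposure on Sweetness Preferences", a reader might infer that showing no effect is half of the trial's question. The stated objective is to assess and compare effects, and no equivalence aim or margin is set.
- A reader might also want a null result judged formally against f = 0.1. That rule cannot be written from this document: 0.1 implies no single pairwise difference (0.245, 0.42 or 0.49 SD), and no SD is given to put it on the 0–100 scale.

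This should be corrected. It does not threaten the validity of the significance test.

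**What to change.** - **Primary outcome.** State that all three between-arm differences in 0–6 month change (LSE–RSE, HSE–RSE, HSE–LSE) will be calculated and reported with 95% CIs whether or not the interaction is significant. The interaction test then governs only the significance claim.
- **Interval level.** State whether these intervals are Bonferroni-adjusted to match the pairwise tests.
- **Other outcomes.** Apply the same rule to the month-6 contrasts.
- **Reading a null.** Interpret it from the reported intervals. Do not add a formal rule for concluding no relevant effect based on f = 0.1.

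The cost is a few sentences in the SAP and one results table. No further data are needed, and the model and its significance test stay as they are.

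### The primary contrasts and their Bonferroni divisor are not fixed, and the 80% power belongs to the overall two-visit test, not to the gated, adjusted arm-pair tests that the plan will run

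*SAP*

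**What the plan says.** The Sample size entry of the SAP states: "The sample size calculation is based on our primary outcome: change in preference score from 0–6 months". The design behind the number is given as "assuming a parallel study with 3 groups, with two repeated measures (baseline vs 6-month, correlation between measures of 0.7", and the result is "We estimate that 147 participants are needed to detect an effect size of 0.1" with "power of 80% at a significance level of 0.05". The type of effect size is not named, and the calculation mentions no multiplicity adjustment. Enrolment is set at 180 to allow for dropout.

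The Primary outcome paragraph under Statistical Analysis specifies a linear mixed model with treatment, time at six visits (baseline and months 1, 3, 6, 7 and 10) and their interaction. It then states: "Our main interest is in the change in preference score between 0 and 6 months of any two intervention groups". The interaction is the condition for going further. If it is significant, the predefined contrasts are "baseline vs. month 6 and LSE vs. RSE vs. HSE with all possible combinations". The paragraph ends: "Subsequent, pairwise post-hoc tests will be Bonferroni adjusted". It gives neither the number of comparisons nor the algebraic form of a contrast.

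**The concern.** The contrast sentence is the only place where the SAP defines the tests behind its main conclusion, and it leaves two things open.

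- **Form of the contrast.** Crossing the single time comparison with the three arm pairs gives three differences in change. Treating two visits and three arms as six means and comparing every pair gives 15 tests, none of which is a difference in change.
- **Divisor.** Bonferroni over 3 puts the per-test level at 0.05/3 = 0.0167. Over 15 it is 0.05/15 = 0.0033.

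Two competent analysts could follow the same text and report different primary tests at different levels.

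Separately, the sample size describes one test and the analysis section runs another. The calculation uses two visits, all three arms together and alpha 0.05. The analysis gates on six visits, then looks at pairs of arms, then adjusts. A reader who carries the 80% over to the comparison of LSE or HSE with the control diet could badly misjudge what a non-significant pair means.

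**Working it through.** **Inputs.** From the SAP: effect size 0.1, three arms at 1:1:1, two measures, correlation 0.7, alpha 0.05, N = 147 (49 per arm) and 180 enrolled (60 per arm). Assumptions: 0.1 is Cohen's f, the SD is equal at both visits, data are complete at baseline and month 6, and the pattern of the effect across arms is as shown below.

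**Step 1: reproduce the plan's figure.** For the group-by-time interaction in a two-visit repeated-measures ANOVA, λ = N·m·f²/(1 − ρ) = 147 × 2 × 0.01/0.3 = 9.8, with 2 and 144 df. Power at alpha 0.05 is 79.8%, and 80% needs N = 148. Alternatives do not fit: the between-group main effect needs 822, the time main effect 120, and an interaction over six visits 84. The stated 147 is therefore the overall 2-df interaction test over baseline and month 6, unadjusted.

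**Step 2: translate f into pairwise differences.** With two visits, f = 0.1 for the interaction means that the arm mean changes have an SD of 0.2 (in units of the outcome SD). Check: 49 × 3 × 0.2²/0.6 = 9.8, the same λ. The variance of an individual change is 2(1 − 0.7) = 0.6.

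- Evenly spaced arms: the step is 0.2 × √1.5 = 0.245 SD, and the extreme pair differs by 0.490 SD.
- One arm differs: that arm is 0.424 SD from each of the other two.

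The standard error of a pairwise difference in change is √(2 × 0.6/49) = 0.156 at 49 per arm and √(2 × 0.6/60) = 0.141 at 60 per arm.

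**Step 3: pairwise power (noncentral t, Bonferroni over three, no gate).**

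| Pattern and pair | Difference (SD) | N = 147 | N = 180 |
|---|---|---|---|
| Evenly spaced, extreme pair (LSE–HSE) | 0.490 | 76% | 85% |
| Evenly spaced, adjacent pair (either arm against RSE) | 0.245 | 20% | 25% |
| One arm differs | 0.424 | 61% | 72% |

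For 80% power at this level, the same differences need 54, 211 and 71 participants per arm.

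**Step 4: the reading with 15 comparisons.** Six means give 6 × 5/2 = 15 pairs: 3 within arm, 3 between arms at baseline, 3 between arms at month 6, and 6 that mix arm and visit. Applying a divisor of 15 to the differences in change at N = 147 lowers the figures to 56% (extreme pair), 8% (adjacent pair) and 40% (one arm differs). These show how much the unstated divisor matters. They are not a forecast.

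**Step 5: the gate.** The interaction over six visits has (3 − 1)(6 − 1) = 10 df, not 2. With compound symmetry at 0.7, evenly spaced arms and N = 147, its power ranged from 64% to 98% over five assumed time courses. A gate can only remove rejections, so the step 3 figures are ceilings for the procedure as written. In the least favourable course, no pair can exceed 64%.

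**Step 6: the alternative.** With the 2-df test of the 0–6 month change as gate and each pair then tested at 0.05, simulation with evenly spaced arms at N = 147 gave about 79% for LSE–HSE and 33–34% for an adjacent pair. The familywise error was 4.8–5.0%.

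**The case against.** The strongest reply is that the contrasts are clear enough in context. One time comparison combined with three arm pairs gives exactly three contrasts. The stated main interest is the 0–6 month change between any two arms, and the interaction is introduced as showing whether change differed by arm. This stands. A reader might infer that the plan leaves out the difference in change, judges arms by within-arm significance, or spends most of its alpha on comparisons nobody wants. The text does not establish any of these. They need the six-mean reading, which is possible but is not the one the context favours, and the SAP states no divisor of 15. What remains is that neither the form nor the divisor is written down.

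A second reply is that the SAP never claims 80% for a pair, that sizing a three-arm trial on the overall test is a legitimate choice, and that 147 is correctly computed for it. All of this stands, so the sample size should not be read as an arithmetical error. But the SAP places its main interest in pairs of arms and gives no power for them.

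A third reply is that the pairwise figures rest on an assumed arm pattern, and that LSE–HSE at 76% is close to 80%. Both are true. The figures for comparisons with control are the sensitive ones, and they move from 20% to 61% with the pattern at N = 147.

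Finally, changing the gate and dropping Bonferroni goes beyond wording, and Bonferroni over three already protects the error rate. That is fair, and it is why Holm or Bonferroni over three remains an acceptable alternative.

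**Conclusion.** The point holds as a defect of specification and of what the power statement covers. The contrast sentence is ambiguous and the divisor is missing. The more natural reading, three differences in change, is the sound one and should be made explicit.

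On either reading, the 80% describes the overall 2-df two-visit test at unadjusted 0.05, not the sequence of a six-visit gate followed by Bonferroni-adjusted pairs. On the favourable reading, with a divisor of three and ignoring the gate, pairwise power at N = 147 runs from 20% to 76% depending on pair and pattern. With all 180 completing it runs from 25% to 85%.

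These figures rest on 0.1 being Cohen's f, which is well supported because it reproduces the stated N to within one participant. They also rest on equal SDs and on the two arm patterns shown, neither of which the SAP states. The six-visit gate figures further assume compound symmetry and particular time courses.

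**What to change.** 1. **Contrasts.** Replace the contrast sentence by three named contrasts of change (month 6 minus baseline) from the mixed model: LSE−RSE, HSE−RSE and HSE−LSE.
2. **Gate and multiplicity.** Gate them on the 2-df test of the 0–6 month treatment-by-time contrast from the same model, and test each at 0.05. With three arms, any two true pairwise nulls imply the third, so this closed procedure controls familywise error. The two changes belong together: the unadjusted level is justified by the 2-df gate, not by the six-visit one. Otherwise, keep an adjustment and state it as Holm or Bonferroni over exactly three.
3. **Sample size.** Say that the 80% applies to the overall 0–6 month test, that 0.1 is Cohen's f (if so), and give the pairwise power under stated arm patterns.

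The cost is SAP text only; no data collection or enrolment changes. There are two downsides. The published pairwise power will look less favourable than 80%. The gate and multiplicity rule also change, so the revision must be dated before the first of the two unblinding steps, when participants are sorted into their still unnamed groups.

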Dietary taste patterns.	Measured with the Taste food frequency questionnaire in % of energy coming from each taste cluster.	Measured at 0, 1, 3, 6, 7 and 10 months.
Dietary taste patterns.	Measured with the Taste food frequency questionnaire in % of food weight coming from each taste cluster.	Measured at 0, 1, 3, 6, 7 and 10 months.
Body weight.	Measured with a weighing scale in kg.	Measured at 0, 1, 2, 3, 4, 5, 6, 7 and 10 months.
Waist-to-hip ratio.	Measured using a stretch-resistant tape.	Measured at 0, 1, 3, 6, 7 and 10 months.
% of body fat mass and lean body mass (fat free mass).	Measured with a dual energy x-ray absorptiometry (DEXA).	Measured at 0, 6 and 10 months.
Variation in interstitial glucose levels.	Measured with glucose monitoring sensor (only measured in a subgroup, of 60 subjects, 20 per intervention arm).	Measured at 0, 6 and 10 months.
Change in fasting glucose, HbA1c, insulin, total cholesterol, low-density lipoprotein (LDL), high-density lipoprotein (HDL), triglycerides levels in blood.	Measured in blood in mmol/L.	Measured at 0, 1, 3, 6, 7 and 10 months.
Concentration of biomarkers in urine related to sugar, low and no calorie sweeteners, protein and salt intake.	Measured in urine in mg/d.	Measured at 0, 1, 3, 6, 7 and 10 months.
Intake levels of foods, food groups and macronutrients.	Measured with 24-hour recalls, in kcal/day.	Measured at 0, 1, 2, 3, 4, 5, 6, 7 and 10 months.
Other Outcome measures		
Outcome Measure	Measure Description	Time Frame
Adverse events.	Self-reported and monitored.	Measured at 0, 1, 2, 3, 4, 5, 6, 7, 8, 9 and 10 months.
Gender.	Self-reported.	Assessed at month 0.
Height.	Measured with a stadiometer.	Assessed at month 0.
Physical activity level.	Measured with the Short Questionnaire to Assess Health enhancing physical activity (SQUASH).	Measured at 0, 1, 3, 6, 7 and 10 months.
Polymorphisms related to sweet taste perception.	Genes will be extracted from collected blood samples.	Assessed at month 0.
Age.	Self-reported.	Assessed at month 0.
Medicine usage.	Number and type of medicine used, self-reported.	Assessed at month 0.

STATISTICAL PRINCIPALS	
Principals and P-values	Prior to data analysis, normality of the data will be inspected. Non-normally distributed data will be transformed or analysed using non-parametric tests, if deemed necessary. Statistical significance is set at $p<0.05$.

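### The interaction gate placed before the Bonferroni-adjusted primary comparisons adds no needed error control and can only lose power

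*SAP*

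**What the plan says.** In the SAP, under Analysis methods (Primary outcome), a linear mixed model is fitted with treatment, time at six levels (baseline and months 1, 3, 6, 7 and 10) and their interaction. The target is stated plainly: "Our main interest is in the change in preference score between 0 and 6 months of any two intervention groups". The order of testing follows. First, "The interaction effect will be evaluated to indicate if the change differed between the groups". Only if that test is significant are the baseline-to-month-6 and between-arm contrasts calculated. Then: "Subsequent, pairwise post-hoc tests will be Bonferroni adjusted". The SAP does not limit the gate to the 0-6 month change and does not give the size of the Bonferroni family.

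Under Sample size, the trial is planned on two visits: "We estimate that 147 participants are needed to detect an effect size of 0.1", with "two repeated measures (baseline vs 6-month, correlation between measures of 0.7" and "power of 80% at a significance level of 0.05".

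**The concern.** Two protections against multiple testing are applied in series to the comparisons that the plan calls its main interest. A pairwise difference must pass its own Bonferroni threshold and also wait for a separate overall test. If one of these steps is enough to hold the error rate, the other only removes true findings. A real difference in 0-6 month change between two diets could then go undeclared because an overall test, possibly spread over visits that are not part of the primary question, missed 0.05.

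**Working it through.** **Inputs from the SAP.** Three arms "at the ratio 1:1:1 to each of the three groups", N = 147 (49 per arm), effect size 0.1, two measures, correlation 0.7, alpha 0.05, power 80%.

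**Assumptions.** The effect size is Cohen's f; the pairwise tests are two-sided; the Bonferroni divisor is 3; the correlation is 0.7 between any two of the six visits; data are complete on 49 per arm.

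**1. The plan's own figure.** Noncentrality = N·m·f²/(1−ρ) = 147 × 2 × 0.01 / 0.3 = 9.8. With 2 and 144 df this gives power 79.8%, so 147 reproduces. It is the sample size for a 2-df, two-visit interaction.

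**2. Is the gate needed for error control?** Three tests at 0.05/3 have familywise error of at most 3 × 0.05/3 = 0.05. From the studentized range with 144 df, the exact value when all arms are equal is 4.4%. Bonferroni alone is sufficient. The planned rule rejects a pair only where Bonferroni rejects it and the gate is also open, so it can never reject more than Bonferroni alone.

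**3. Degrees of freedom of the gate.** As written, (3−1) × (6−1) = 10. Restricted to baseline and month 6, it would be 2.

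**4. Effect sizes simulated.** Month-6 change in units of the SD of change, both at noncentrality 9.8:
- Evenly spaced arms (−0.316, 0, 0.316): 49 × (0.1 + 0.1) = 9.8.
- One arm differs (0, 0, 0.548): 49 × 0.3 × 2/3 = 9.8.

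For the six-visit gate the noncentrality is 2 × 9.8 × S = 19.6·S, where S is the sum of squares of the time profile about its six-visit mean. A two-visit profile (0, 1) has S = 0.5 and returns 9.8.

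**5. Cost of the gate.** Power in %, Bonferroni alone → gate plus Bonferroni. There were 400,000 simulated trials per 2-df scenario and 200,000 per 10-df scenario, so the simulation error is about 0.1 point. Profiles give the effect at months 1/3/6/7/10 as a percentage of the month-6 effect.

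| Gate and profile | 19.6·S | Gate opens | Each true pair, one arm differs | LSE vs HSE, evenly spaced |
|---|---|---|---|---|
| 2 df, 0-6 month change | – | 80 | 61.3 → 61.2 | 76.0 → 75.6 |
| 10 df, 100/100/100/0/0 | 29.4 | 98 | 62.2 → 62.0 | 76.7 → 76.3 |
| 10 df, 0/0/100/0/0 | 16.3 | 80 | 62.1 → 56.8 | 76.7 → 68.2 |
| 10 df, 33/67/100/50/0 | 15.0 | 75 | 62.1 → 55.2 | 76.7 → 66.1 |
| 10 df, 33/67/100/67/33 | 12.1 | 64 | 62.2 → 50.1 | 76.6 → 58.3 |

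The loss grows as the effect is spread over more visits, because S shrinks while the month-6 contrast does not change. For neighbouring arms in the evenly spaced case, Bonferroni power is only about 20%, and the 10-df gate takes up to about 2 points from it. Under the complete null, the planned rule with a 10-df gate has familywise error 1.2%, against 4.4% for Bonferroni alone.

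**6. Can Bonferroni be dropped instead?** With three arms, if two pairwise equalities hold, the third holds too. A 2-df test of equal 0-6 month change followed by unadjusted pairs is therefore a closed test: error 5.0% under the complete null and 5.0% for the equal pair when the third arm is far away. This fails for the six-visit gate. If the arms differ at months 1 and 3 only, that gate opens in 96% of trials, and unadjusted pairs then give 12.1% familywise error at month 6, against 4.3% with Bonferroni.

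**7. Valid alternatives.** Power in the two-visit setting, as planned (2-df gate plus Bonferroni) / ungated Holm / 2-df closed test:
- Each true pair, one arm differs: 61 / 65 / 72.
- LSE vs HSE, evenly spaced: 76 / 77 / 79.
- Neighbouring arms, evenly spaced: 20 / 25 / 33.

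Holm rejects everything that Bonferroni rejects, hence everything the planned rule rejects, and holds the error at 5% (4.4% under the complete null, 5.0% with two arms equal and the third far away). Against the planned rule with the 10-df gate, Holm's gain for LSE vs HSE reaches 77.3 − 58.3 = 19 points in the last profile of the table.

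**The case against.** The planned rule makes no inferential error: familywise error stayed below 5% in every scenario computed. If the gate is meant as a 2-df test, placing it before Bonferroni costs almost nothing (61.3% to 61.2% per true pair). The gap between 61% and 72% should not be charged to the double step; it is the cost of using Bonferroni instead of a closed test. The large losses arise only with the 10-df gate and only for some effect profiles. All of this stands, and it makes the point one of efficiency.

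A reader might go further and infer that, with three arms, either protection alone holds 5%, so that the Bonferroni step is the redundant one. The SAP does not support that. Its model has six visits and its gate is not restricted to the 0-6 month change; on that reading Bonferroni is the step that protects month 6. The contrasts are also described as all possible combinations, which may include within-arm changes from baseline. These would break the three-hypothesis argument even behind a 2-df gate: with two arms unchanged and one far away, testing the one between-arm and two within-arm true nulls unadjusted gives 11.4% familywise error.

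It can also be said that the trial was sized on an interaction test, so that test deserves a place. It can be reported, but the SAP names the pairwise 0-6 month changes as its main interest, and the sizing used two visits, not six.

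**Conclusion.** The point holds as a matter of lost power, not of validity. Once the three pairs are Bonferroni adjusted, the gate contributes nothing that is needed to keep familywise error at 5%, and it can only remove rejections. Its cost is under 0.5 point if it is a 2-df test of the 0-6 month change. Under the literal six-visit reading it is about 0.5 point or less when the effect is equal at months 1, 3 and 6 and then gone, about 5 to 9 points when it is present at month 6 only, and up to about 18 points in the build-up-then-fading profiles examined. These ranges refer to the true pairs when one arm differs and to LSE vs HSE when the arms are evenly spaced.

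The figures rest on the assumptions listed in the working. The last figure depends on the chosen time profile and is not an upper bound. That the gate cannot help power, and that ungated Holm rejects at least whatever the planned rule rejects, needs none of those inputs beyond a family of these three pairs.

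**What to change.** In the SAP, Analysis methods (Primary outcome), remove the condition of a significant interaction for the primary contrasts and replace the Bonferroni sentence. Suggested text: *The three between-arm differences in 0-6 month change (LSE-RSE, HSE-RSE, HSE-LSE) are estimated from the mixed model and tested directly, with Holm adjustment at a familywise level of 0.05. The overall treatment-by-time interaction and the within-arm changes are reported descriptively.* This also settles the family size.

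Alternative: replace both the gate and the Bonferroni sentence by a 2-df test of equal 0-6 month change in the three arms at 0.05, followed, if significant, by only these three pairs, each at 0.05 without adjustment. Changing the Bonferroni sentence alone is not enough, because the six-visit condition would remain in front; dropping the adjustment while that condition stays would be wrong.

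The cost is a few lines of SAP text and no extra data. Unadjusted 95% intervals for the pairs are not simultaneous and should be labelled so.
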